6.6.3. Surgery

Surgery will occur on Day 0. Standard of care procedures should be followed.

6.6.4. Treatment Period/Post Surgery

Patients will receive their first dose of study medication (T₀) within 8 hours of meeting the postsurgical eligibility. Treatment is anticipated to occur from Hours 0 up to Hour 168. The latest (last dose) that is allowed is at Hour 164. Patients will be dosed at Hour T₀, T₂, T₄, and then every 4 hours thereafter, for a total of up to 43 doses administered over the 168-hour treatment period. Assessments will have a ± 10 minute window.

Antiemetic treatments (with the exception of Zofran or other 5-HT₃ antagonists) are allowed.

Treatment period assessments include:

- Recording vital signs including: respiratory rate, heart rate, pulse oximetry (SpO₂), temperature, and blood pressure at 0, 0.5, 1, 2, 3, 4, and then every 4 hours thereafter during the first 48 hours. After 48 hours patients continuing treatment should have vitals taken every 8 hours.
- ECGs will be assessed at screening, post-surgery prior to dosing (T₀), and at 20 to 30 minutes after the start of each infusion for the first 24 hours. With the 10-minute window allowed per assessments, the on-treatment ECGs need to be done between 10 to 40 minutes after the start of each dosing infusion.
- Patient Global Assessment at 24 hours
- Adverse events and concomitant medications will be collected as appropriate.
- Following the first dose of study drug, the patient will be allowed to use non-opioid analgesics if additional pain relief is required. These medications will be captured on the concomitant medications page
- Concomitant medication use

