
Statistical methods:
 
Sample Size
 
A sample size of approximately 250 patients will be enrolled. This sample size of 250 patients will provide approximately 90% power to detect at least one incidence of uncommon adverse events (those events with a true underlying incidence of 1%).
 
General Statistical Methods
 
This is an open-label study in which the objective is to assess the safety of Tramadol for post-surgical pain in patients having elective surgery. The statistical methods utilized will be consistent with this objective.
 
Outcomes will be tabulated utilizing descriptive methods only (e.g., mean, standard deviation, median, min, max for continuous variables, and number and percent for categorical variables).
 
The baseline for all variables will be the last measurement obtained prior to the patient receiving the first dose of study drug.
 
Patient disposition (including the number and percent of patients who are enrolled, who receive treatment, who prematurely discontinue and reasons for discontinuation, and who complete the study) will be tabulated. The number (%) of patients by exposure (number of doses given, total dose given, time from first dose to last dose) will be tabulated.
 
Study Populations
 
The Safety Population is defined as all patients who receive at least one dose of study medication. This will be the primary population for which conclusions will be drawn.
 
Alpha Levels
 
No inferential testing is planned for this safety-based study. If inferential statistics are used, they will only be applied to allow for better understanding of any treatment effects, but will not be used for hypothesis testing.

Protocol AVE-901-104 Phase 3 Open-Label Safety Study
Avenue Therapeutics, Inc.

Tramadol Infusion
August 29, 2018

Name of Sponsor/Company: Avenue Therapeutics, Inc.
Name of Investigational Product: AVE-901 (Tramadol)
Name of Active Ingredient: Tramadol for intravenous infusion

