6.5. Schedule of Events

Table 4 provides the schedule of events. Note that patients who discontinue treatment at any time after receiving their first dose of study drug (T0) will have all End of Treatment assessments performed.

Protocol AVE-901-104 Phase 3 Open-Label Safety Study
 Avenue Therapeutics, Inc.

Tramadol Infusion
 August 29, 2018

Table 4. Schedule of Assessments for each Study Period (Study AVE 901-104)

Assessments	Screening Day -28 to Day -1 ⁴	Pre-op Day -1/0 ⁴	Surgery Day 0	Treatment Hours Post Start of First Infusion Hour 0 to Hour 164 (assessments ± 10 minute window)							End of Treatment (completed prior to discharge)	Phone Call Day 14±2
				0	0.5	1	2	3	4	Every 4 hours		
Informed Consent	X										EoT	
Medical History	X	X										
Demographic Data	X											
Height and Weight (BMI)	X											
Physical Examination	X	X									X	
ASA Physical Status	X	X										
Vital Signs (and SpO2) ¹	X	X		X	X	X	X	X			X	
Pregnancy Test ²	X	X									X	
Hem/Chem/Urinalysis ³	X										X	
12-Lead ECG	X		X ⁵					X			X	
Eligibility Criteria	X	X										
Surgery			X									
Study Drug Admin				X					X			
PGA				X						X (24 hours only)		X
Adverse Events										X (ongoing)		
Prior/Comments										X (ongoing)		

¹ Post 48 hour treatment, vitals drawn only every 8 hours
² Screening and End of Treatment Pregnancy test (serum) by central laboratory, Pre-op pregnancy test (urine) conducted locally for female patients of childbearing potential.
³ Hematology, Chemistry, Urinalysis sent to central laboratory for analysis. Patients screened and not receiving results from central labs prior to surgery may have local lab done to assess eligibility.
⁴ If necessary, Screening and Pre-Op procedures may be combined into one visit assessment for time considerations associated with scheduled surgeries. Screening Visit procedures should take precedent.
⁵ ECG should be taken post-surgery, prior to dosing at T0

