3. GENERAL ANALYSIS AND REPORTING CONVENTIONS

This section discusses general policies to be employed in the analysis and reporting of the data from the study. Departures from these general policies are provided in the specific detailed sections of this SAP. When this situation occurs, the rules set forth in the specific section take precedence over the general policies.

All continuous study assessments will be summarized by time point (as applicable) using the descriptive statistics n, mean, SD, median, and range (minimum, and maximum). All of the categorical study assessments will be summarized by time point (as applicable) using frequency counts and rates of occurrence (%).

The treatment group will be labeled as '**Tramadol 50 mg**' for all outputs. All study data will be listed by study center, patient, and time point (as applicable).

No preliminary rounding will be performed; rounding will only occur after the analysis. To round, consider the digit to the right of the last significant digit: if <5, then round down; if \geq 5, then round up. Means and medians will be presented with one more decimal place than the precision of the raw data. Standard deviations will be presented with two more decimal places than the precision of the raw data. Percentages will be presented with one decimal place. Minimums and maximums will be presented with the same precision as the original data.

All analyses will be performed using the SAS System® version 9.3 or higher. The domain (Study data tabulation Model [SDTM]) and analysis (Analysis Data Model [ADaM]) data sets will be taken as input to the SAS programs that generate the report-ready tables, figures and listings. The submission ready SDTM and ADaM data sets will be provided to the sponsor along with display deliveries.

The following conventions will be used throughout the study analysis:

- Time T0 is the time of start of the first study drug administration.
- Study Day is defined as (Date of Assessment minus Date of First Dose of Study Medication). The first day of dosing is Study Day 0. The day immediately prior to first dose is Study Day -1. Study Day will be calculated for every record in the database and presented alongside the date fields in the data listings, where applicable. For instance, the start *date* of each TEAE will also have the Start *Day* presented in the listings.
- Assessment and visit times are defined relative to time T0.

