- Baseline value is defined as the last valid measurement prior to the first treatment administration.
- Change from baseline is defined as post-baseline value minus baseline value.
- Unscheduled visits and measurements will be included in subject listings but will not be used in analyses.

- If duplicate values are obtained at a given visit (e.g., lab assay is repeated on a sample resulting in two results, or vital sign repeated during a visit), the last reported value will be used unless it is noted that the measurement was in error for that value.
- Values that compromise interpretation will not be used in summaries (e.g., values that were obtained post-dose will not be summarized as pre-dose values).

4. **PATIENT SUMMARIES**

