9.5. Vital Signs

Vital signs results including BP (systolic and diastolic), heart rate, respiration rate, pulse oximetry, and temperature will be listed for individual patients. Baseline for vital signs measurements will be defined as the last evaluation before dosing with study medication. Vital signs and changes from baseline will be summarized by time point.

Vital sign parameter outcomes will be assessed for potential clinical significance; observed values and changes from pre-treatment to on-treatment time points will be tabulated for continuous parameters, as warranted.

The number and percent of patients with potentially clinically significant (PCS) values during the treatment phase will be summarized. A focus will be on new-onset PCS values, i.e., patients with pre-existing PCS values at pre-treatment will not be considered to have new-onset values on-treatment. The criteria for identifying potentially clinically significant vital signs values are provided in Table 4.

Table 4:List of Potentially Clinically Significant Ranges for Vital Sign Parameters
(Study AVE-901-104)

Variable Name	LOW	HIGH

Systolic BP	<86 mm Hg OR a decrease of ≥25 mm Hg from baseline	>200 mm Hg OR an increase of ≥25 mm Hg from baseline
Diastolic BP	<48 mm Hg OR a decrease of ≥20 mm Hg from baseline	>110 mm Hg OR an increase of ≥20 mm Hg from baseline
Heart rate ¹	1) <45 bpm OR a decrease of ≥25 bpm from baseline	1) >105 bpm and increase ≥25 bpm from baseline OR >125 bpm

¹ bpm: beats per minute

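### The ±10-minute window lets Hour 0 vital signs be taken after the first infusion starts, so vital-sign baselines could mix post-operative and pre-operative readings

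*Protocol*

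**What the plan says.** - **Schedule.** Protocol 6.6.4 asks for vital signs, including SpO2, "at 0, 0.5, 1, 2, 3, 4, and then every 4 hours thereafter during the first 48 hours". The last scheduled set before that is the Pre-op one, within 24 hours of the planned start of surgery (6.6.2). The Surgery column of protocol Table 4 lists no vital signs.
- **Window.** 6.6.4 states: "Assessments will have a ± 10 minute window". The treatment-block header of Table 4 says the same, "Hour 0 to Hour 164 (assessments ± 10 minute window", and that block includes the Hour 0 column.
- **Time zero.** SAP 3: "Time T0 is the time of start of the first study drug administration".
- **Contrast with the ECG.** Table 4, footnote 5: "ECG should be taken post-surgery, prior to dosing at T0". Vital signs have no such footnote.
- **Baseline.** Protocol synopsis: "The baseline for all variables will be the last measurement obtained prior to the patient receiving the first dose of study drug". SAP 9.5: "Baseline for vital signs measurements will be defined as the last evaluation before dosing with study medication".
- **Late readings.** SAP 3 rules that "values that were obtained post-dose will not be summarized as pre-dose values". The same list keeps unscheduled measurements in the listings but out of the analyses.

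**The concern.** The Hour 0 set is the only scheduled vital-sign set between the end of surgery and the first dose, so it is the natural post-operative reference. Yet the window allows it to be taken while drug is already running. A site can follow the schedule exactly and still leave a patient with no scheduled post-operative, pre-drug reading.

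Vital-sign change is a named safety endpoint under the primary objective (protocol 5, SAP 2.1.1). The baseline feeds the change tables and the potentially clinically significant (PCS) limits in SAP Table 4 that are defined by change: 25 mm Hg systolic, 20 mm Hg diastolic and 25 bpm. It may also affect the absolute limits, because SAP 9.5 counts a value as new-onset only if the patient had no such value before treatment. If pre-treatment status is read from the Pre-op set, a low pressure already present after surgery but before drug could be counted as new on drug. No control arm is available to subtract the effect of surgery, anaesthesia and pain.

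**Working it through.** The plan attaches no figure to the vital-sign baseline, so there is nothing to reproduce on this point. Its one sample-size figure, about 90%, reproduces as 1 − 0.99^250 = 0.919 and does not depend on the baseline.

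**Tracing the rules for two compliant patients**

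1. Patient A has Hour 0 vital signs at −5 minutes. The reading is before dosing, so baseline is post-operative.
2. Patient B has them at +5 minutes. This is inside the window, but the infusion has started, so SAP 3 does not allow the value as pre-dose. The previous scheduled set is Pre-op, so on scheduled data alone baseline is pre-operative.

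**Is a reading inside the window really on drug?** The infusion lasts 15 ± 4 minutes (SAP 2.5.1), that is 11 to 19 minutes. At +10 minutes and a constant rate, the share of the 50 mg dose given is 10/15 = 67% (33 mg), with a range from 10/19 = 53% (26 mg) to 10/11 = 91% (45 mg). Such a reading cannot be treated as pre-dose.

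**Is the two-sided window meant literally?** The protocol writes its exceptions out. The T0 ECG must precede dosing, End of Treatment assessments are exempt from the window (6.6.5), and on-treatment ECGs due at 20 to 30 minutes are explicitly widened on both sides to 10 to 40 minutes (6.6.4). Hour 0 vital signs have no exception.

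**Number of patients.** The documents give no distribution of measurement times. Assumed late shares of 10%, 25% and 50% of 250 are 25, about 63 and 125 patients. The 50% figure is what timing spread evenly over −10 to +10 minutes would give (10 of 20 minutes).

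**Effect on the systolic flag (illustration; shift and SD are assumed).** Let the change from a post-operative baseline be normal with mean 0, and let surgery and pain raise pressure by δ over the Pre-op value. For one on-treatment reading against a Pre-op baseline:

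P(flag) = Φ((−25 − δ)/SD) + 1 − Φ((25 − δ)/SD)

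- SD 12, δ = 0: 0.0186 + 0.0186 = 0.0372
- SD 12, δ = 10: 0.0018 (falls) + 0.1056 (rises) = 0.1074
- SD 12, δ = 15: 0.0004 + 0.2023, about 0.203
- SD 10: 0.0124 at δ = 0, 0.0670 at δ = 10
- SD 15: 0.0956 at δ = 0, 0.1685 at δ = 10

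With SD 12 and δ = 10, flagged rises go from 1.9% to 10.6%, while flagged falls go from 1.9% to 0.2%. The error therefore runs both ways: it adds rises and hides falls. A negative δ reverses this.

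Across the study, with late share s, the flagged proportion is (1 − s) × 0.0372 + s × 0.1074. This gives 0.0442 at s = 10% and 0.0723 at s = 50%, or about 11 and 18 of 250 patients, against 250 × 0.0372 = 9.3 when nobody falls back.

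**The case against.** **The baseline rule is consistent.** Protocol and SAP both take the last measurement before first dose, which gives one baseline per patient. That stands. A reader might infer that the plan names Hour 0 as the post-operative baseline and then discards it, but no text names it so. A late value loses only its pre-dose role. It is still listed, and SAP 7.2, which summarises by nominal visit, leaves unclear whether it would appear in an Hour 0 row.

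**Recovery-room readings might serve.** SAP 3 bars unscheduled measurements from analyses, but it also says that specific sections override its general policies. SAP 9.5 and the protocol synopsis do not limit baseline to scheduled readings. So the fallback to Pre-op is not certain. Equally, SAP 9.5 does not expressly admit unscheduled values. The text is ambiguous, and that is itself a reason to settle it.

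**Respiratory rate and SpO2 are checked after surgery anyway.** Protocol 7.2.1 requires a post-operative evaluation before the first dose that covers both. It would be wrong to say that no such pre-drug check exists. However, first dose may follow up to 8 hours after eligibility is met (6.6.4), the check is not a scheduled set in Table 4, and its criteria set no blood-pressure or heart-rate limits. SAP Table 4 has no PCS criterion for respiratory rate or SpO2, so no flag on those is at risk.

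**The consequence is limited.** The analysis is descriptive, the absolute limits themselves do not use baseline, and the high heart-rate change limit also requires more than 105 bpm. Even a sound post-operative baseline leaves recovery from anaesthesia confounded with drug in a single-arm study. All of this stands and keeps the point modest.

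**Conclusion.** The gap is real. Followed exactly, the schedule allows a patient's only scheduled post-operative, pre-drug vital signs to be taken on drug. Baseline then falls back to a pre-operative reading, unless an unscheduled post-operative one is accepted. Vital-sign changes and the change-based blood-pressure and heart-rate flags could then mix two clinical states, with surgical effects counted as on-treatment change or masking it.

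The size cannot be determined from the documents. A reader might infer that about half of all baselines are affected, but that assumes measurement times spread evenly over the window, for which the plan gives no basis; staff may often measure before starting the pump. The 25 to 125 patients and the flag rates above are conversions of assumed inputs, not estimates. Adverse-event counts and the ECG baseline, including QTcF, are not affected. The point is worth fixing because it touches a named safety endpoint, there is no control arm, and protocol 4.4 plans to combine these data with those of two other studies.

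**What to change.** - **Protocol Table 4 and 6.6.4.** State that Hour 0 vital signs and SpO2 are taken after surgery and before the first infusion starts, with no plus side to the window, as is already required for the T0 ECG. The sponsor sets the length of the pre-infusion interval.
- **SAP 9.5.** Define the vital-sign baseline as the last post-surgery, pre-infusion reading, scheduled or not, and state that this overrides the unscheduled-measurement rule in SAP 3. Flag patients with no such reading.

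The cost is a footnote, a matching line in 6.6.4 and a sentence or two in the SAP. No measurement is added, and the sample size is unchanged. The protocol line helps only patients not yet dosed. The SAP change can be made until sign-off before database lock (SAP 1). The small downside is that a few patients may be flagged as having no post-operative baseline.

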
Protocol AVE-901-104 Phase 3 Open-Label Safety Study
Avenue Therapeutics, Inc.

Tramadol Infusion
August 29, 2018

Name of Sponsor/Company: Avenue Therapeutics, Inc.
Name of Investigational Product: AVE-901 (Tramadol)
Name of Active Ingredient: Tramadol for intravenous infusion

18. The patient was administered an investigational drug product within 30 days prior to Screening.
 
19. The patient has previously participated in a clinical study with AVE-901.
 
POST SURGICAL EXCLUSION CRITERIA
 
The patient is to be evaluated post-operatively prior to the initial treatment with the study drug and will be withdrawn prior to treatment with the study drug if any of the following exclusion criteria are met:
 
 1. Patients who, in the opinion of the investigator, are not likely to tolerate the protocol's allowed analgesic regimen (tramadol plus non-opioid adjuvants). 2. Patients who have been admitted to the ICU post-surgery or have experienced complications during the surgical procedure that would put them at increased risk from receipt of the investigational product in the opinion of the investigator. 3. The patient is not clinically stable and not able to answer questions and follow commands. 4. The patient has evidence of respiratory insufficiency, such as a respiratory rate that is less than 8 breaths per minute or arterial oxygen saturation by pulse oximetry of less than 90% with supplemental oxygen. 5. Use of 5-HT3 antagonists (e.g. ondansetron, granisetron, palonosetron) preoperatively, intraoperatively, or postoperatively

Investigational product, dosage and mode of administration:
 
AVE-901, 50 mg. Assigned study treatment (51 mL) doses will be administered IV over 15 minutes (+/- 4 minutes) via infusion pump. A trained health care professional will flush the line with normal saline at the end of each infusion.

Duration of treatment:
 
Study drug will be administered for up to 7 days following initiation of the first dose.
 
Total patient participation in this study, from initial screening through the final assessment, is expected to be between 1 and 7 weeks.

Reference therapy, dosage and mode of administration:
 
None.

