12.1. Sample Size Considerations

A sample size of approximately 250 patients will be enrolled. This sample size of 250 patients will provide approximately 90% power to detect at least one incidence of uncommon adverse events (those events with a true underlying incidence of 1%).

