7.2. Assessment Time Windows

Summaries will be based on the nominal protocol-specified visits as appropriate.

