9.7. ECG Examinations

ECG examination interpretation results and heart rate and interval duration results will be listed for individual patients. Baseline for ECG continuous measurements will be defined as the last evaluation before dosing with study medication. Continuous ECG values and changes from baseline will be summarized by time point. The proportion of subjects with Normal, Abnormal: Not Clinically Significant, and Abnormal: Clinically Significant will be summarized by time point.

The ECG analysis will include a careful review of QTcF values. As part of this review, a summary of the number (percent) of patients with QTcF values in the following ranges will be provided: \leq 450 msec, >450 to \leq 480 msec, >480 to \leq 500 msec, and >500 msec. This will be performed by visit as well as at ANY time during the treatment period (where the highest QTcF value will be used for that assessment).

The incidence of PCS values will be presented, with a focus on new-onset PCS values. The criteria for identifying potentially clinically significant ECG values are provided in Table 5.

Table 5:List of Potentially Clinically Significant Ranges for ECG Parameters (Study
AVE-901-104)

PR Interval	
High: >200 msec OR Increase ≥ 20 msec from baseline	
QRS Interval	
High: >100 msec OR Increase ≥ 10 msec from baseline	
QT Interval	
High: >500 msec OR Increase ≥ 60 msec from baseline	
QTcF Interval	

High: > 450 msec (Males); >470 msec (Females) OR Increase \geq 50 msec from baseline	;
--	---

Heart Rate

Low: <45 bpm OR a decrease of \geq 25 bpm from baseline

High: >105 bpm and increase \geq 25 bpm from baseline OR >125 bpm

Tramadol Infusion 07FEB2019

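### The ±10-minute window makes on-treatment ECGs compliant from minute 10, before any permitted infusion has ended, and the SAP does not separate these ECGs

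*Protocol*

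**What the plan says.** **Infusion length.** The Protocol Synopsis (investigational product) and SAP 2.5.1 both say that "doses will be administered IV over 15 minutes (+/- 4 minutes) via infusion pump".

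**ECG timing.** Protocol 6.6.4 places on-treatment ECGs "at 20 to 30 minutes after the start of each infusion for the first 24 hours". The same section sets a general rule: "Assessments will have a ± 10 minute window". It applies that rule to the ECGs itself and concludes that "the on-treatment ECGs need to be done between 10 to 40 minutes after the start of each dosing infusion".

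**Analysis.** SAP 7.2: "Summaries will be based on the nominal protocol-specified visits as appropriate". SAP 9.7: "Continuous ECG values and changes from baseline will be summarized by time point". SAP 9.7 also tabulates QTcF categories by visit and at any time during treatment, "where the highest QTcF value will be used for that assessment". Neither section uses the actual ECG time relative to the end of the infusion.

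**The concern.** The target of 20 to 30 minutes clears even the longest permitted infusion, so as targeted every on-treatment ECG sees the whole of that dose. The target is already a 10-minute range. Adding the general window to both ends triples it and moves the lower edge to a point where the dose is still running in. Neither document gives a reason for sampling during the infusion.

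ECG changes are among the safety endpoints in Protocol 5 and SAP 2.1.1, and SAP 9.7 gives QTcF particular attention. If an ECG effect rises with exposure, ECGs taken during the infusion and summarized under the same time point would pull the mean change toward zero. In a safety study that is the less cautious direction. Protocol 4.4 also says that these data will join those of two efficacy studies in one safety database.

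**Working it through.** **Inputs**
- Infusion length: 15 ± 4 min (Protocol Synopsis; SAP 2.5.1).
- ECG target: 20 to 30 min after infusion start; window ±10 min (Protocol 6.6.4).
- Infusions in the first 24 h: Hours 0, 2, 4, 8, 12, 16 and 20, which is 7, or 8 if Hour 24 is counted.
- Assumption: constant pump rate.

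**1. The plan's own interval.** 20 − 10 = 10 and 30 + 10 = 40. The stated 10 to 40 minutes is reproduced.

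**2. Infusion end.** 15 − 4 = 11 and 15 + 4 = 19. The target (20 at the earliest) is later than the latest end (19). The lower edge of the window (10) is earlier than the earliest end (11).

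**3. Size for an infusion of T minutes.** The permitted window is 40 − 10 = 30 min long.

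| | T = 11 | T = 15 | T = 19 |
|---|---|---|---|
| Dose delivered at minute 10: 10/T | 91% | 67% | 53% |
| Share of window before infusion end: (T − 10)/30 | 3% | 17% | 30% |
| Early ECGs per patient, even spread: 7 to 8 × that share | 0.2 to 0.3 | 1.2 to 1.3 | 2.1 to 2.4 |
| Undelivered dose averaged over all ECGs, even spread: (T − 10)²/(2 × T × 30) | 0.2% | 2.8% | 7.1% |

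For example, at T = 15 the last row is 25/(2 × 15 × 30) = 25/900 = 2.8%. At T = 19 it is 81/(2 × 19 × 30) = 81/1140 = 7.1%.

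**4. Range around the even spread.** The documents do not say where in the window ECGs fall. If all are done at the 20 to 30 minute target, the undelivered dose is 0. If all were done at minute 10, it would be 1 − 10/T, that is 9%, 33% or 47%. The even spread lies between these and is not a worst case.

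**5. Carry-over after the first dose.** In Protocol Table 3 the 50 mg IV regimen has a mean Cmax(44-48) of 711 ng/mL and a 48-hour value of 448 ng/mL, a difference of 263. Assume that concentration rises in a straight line from 448 to 711 during the infusion. Minute 10 is then about 448 + (10/15) × 263 = 623 ng/mL, or 88% of the peak, for a 15-minute infusion. For 19 minutes it is 448 + (10/19) × 263 = 586 ng/mL, or 82%. Late in treatment the exposure gap is therefore smaller than the dose fractions suggest. At the first infusion there is no earlier study dose, so this cushion is absent.

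**6. Lower limit that would clear every infusion.** A fixed limit has to be at least 19 min, an early allowance of at most 1 min before minute 20. A limit of 15 min clears the 15-minute infusion but not the 19-minute one.

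**The case against.** The strongest reply is that the interval is an open choice. The protocol works out 10 to 40 minutes and prints it, times ECGs from infusion start, and never calls them post-infusion. That stands: this is a weakness of design, and the documents do not contradict themselves.

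Second, harm requires the ECG effect to be smaller during the infusion than later in the window. The documents give no effect size, no time of peak effect and no relation between concentration and QTc. An ECG at minute 40 might also miss a peak near infusion end. This stands too, and it is why the bias cannot be given a size.

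Third, the plan has partial safeguards. The any-time maximum draws on repeated ECGs as drug accumulates, and SAP 9.1 provides ongoing central reading for each patient. These lessen the problem but do not protect the by-time-point summaries. SAP 3 also keeps values that compromise interpretation out of summaries. That clause is general, and its example is a post-dose value labelled as pre-dose, so it does not clearly reach an ECG that complies with the protocol.

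A reader might infer three stronger things that the documents do not support:
- That the window weakens a test of QTcF. The objectives name ECG changes in general, QTcF enters through SAP 9.7, and Protocol 12.8 and SAP 7 plan no inferential testing.
- That all 7 to 8 on-treatment ECGs are affected. That is the total number per patient.
- That the 53% to 91% figures describe a typical ECG. They hold only at exactly minute 10.

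**Conclusion.** The point holds as a small improvement to the design. It follows directly from the stated times that a fully compliant ECG can be recorded before the dose has been delivered, and that no rule in the SAP separates such ECGs.

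The likely effect is modest. It is confined to ECGs done early in the window and would be largest at the first infusion. The averaged dose shortfall of about 3% to 7% rests on a constant pump rate and an even spread of ECG times. Most ECGs may well fall nearer the 20 to 30 minute target, which would make it smaller. The shortfall in dose cannot be turned into milliseconds of QTcF from these documents.

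**What to change.** **Protocol 6.6.4.** State that each on-treatment ECG is done no earlier than the end of that infusion, and keep the 40-minute upper limit. The infusion itself is unchanged.

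**SAP 9.7.** Keep every ECG in the main by-time-point summaries and in the any-time maximum, so that no compliant safety data are dropped. Add one sensitivity by-time-point summary that leaves out ECGs recorded before the actual end of the infusion, where both times are recorded. SAP 6 fills a missing end time as start plus 15 minutes. An imputed end could misclassify an ECG, so the sensitivity summary should use recorded end times only. The documents do not confirm that the clock time of each ECG is captured, and this should be checked first.

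**Cost.** A slightly tighter window for sites, a few more out-of-window records, one sentence in the protocol and one extra table.
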